The goal is to collect adequate PET scan data for at least 2 participants per cohort. Up to four participants in each cohort may participate in the Receptor Occupancy Sub-study. These participants will undergo an MRI during screening and three [¹⁸F]FPEB PET Scans. PET scans will occur at screening (within 60 days of study drug administration), approximately 4 hours post-dose and approximately 24 hours post-dose. The timing of post-dose PET scans may be adjusted after review of human PK data collected in this study. Each participant may be asked to repeat up to one [¹⁸F]FPEB PET scan if a scan fails quality control for a total of up to four [¹⁸F]FPEB PET scans during the course of study participation. The baseline [¹⁸F]FPEB PET scan may be done after the inpatient and clinic follow-up visits if needed.

The rationale for enrolling up to four participants from each Cohort in the sub-study is to help ensure that quality [¹⁸F]FPEB PET scan data is collected at all three timepoints on at least two participants per cohort. This over-enrollment is necessary due to possibility of failed [¹⁸F]FPEB PET tracer synthesis and the time sensitive nature of the post-dose [¹⁸F]FPEB PET scans. The goal is to collect adequate PET scan data for 2 participants per cohort. We will not scan additional participants per cohort once adequate scan data has been captured.

MRI Procedures

Magnetic Resonance Imaging (MRI) will be performed for enrollment in the receptor occupancy substudy. To be screened by MRI, participants must meet all clinical eligibility criteria. MRI will be used for quantitative evaluation

of PET scans, to screen for anatomical abnormalities, and to screen for neurological disease. MRI exclusion criteria will consist of focal or global atrophy, evidence of chronic or acute cerebrovascular disease, any space occupying lesion or other indication of underlying pathology. All MRIs will be read by a local expert to ensure consistent interpretation. MRIs will take place at the Anlyan Center, [name].

MRI will be performed on a 3 Tesla system using pulse sequences selected to accommodate clinical reading, anatomical identification of VOIs, gray/white matter segmentation, and registration to a common space. Sequences will include:

- 3 Plane/Tri-Planar Scout
- Axial T2 Star/GRE
- Axial T2 FLAIR
- Axial fcMRI (Participant should have eyes OPEN)
- Sagittal 3D Accelerated MPRAGE/IRSPGR
- Axial DWI
- Axial DTI
- Axial PASL (eyes open)

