- High Resolution Hippocampal T2

PET Scan Procedures

PET scanning sessions will take place at the Yale University PET Center, [name]. Participants with history of prior radiation exposure within the past year such that participation in this study would place them over FDA limits for annual radiation exposure will be excluded from this study.

Arterial Line Placement: A radial artery catheter will be inserted by an experienced provider before the PET scan to draw arterial blood samples for metabolite analysis and for determination of the fraction of plasma radioactivity unbound to protein. The goal of the arterial line is to be able to measure absolute physiological functions by mathematically relating the signal (from the PET scanner) to the tracer availability (from the blood). This approach is the gold standard for obtaining quantitative PET data and is required for receptor occupancy studies using orally administered drug. In scenarios where the arterial line cannot be placed or maintained, an additional intravenous catheter may be placed for blood sampling.

Radiotracer Injection: At each PET scanning session, participants will receive ≤ 5 mCi of $[^{18}\text{F}]$ FPEB administered by bolus injection via a venous catheter. The participant's head will be immobilized and a transmission or CT scan will be obtained and used for attenuation correction. Vital signs will be taken immediately prior to injection of $[^{18}\text{F}]$ FPEB and will be monitored during the scan. Any adverse events will be evaluated and recorded continuously through the PET imaging visit.

Scanning Session: The scanning period is 0 - 120 min post injection. Dynamic images of radioactivity concentration are reconstructed with corrections for attenuation, normalization, random events, scatter, and dead time.

Post-Scan: Upon completion of the PET Scanning days, the IV and arterial catheter will be removed and local pressure applied at the arterial catheter site for a minimum of 15 minutes to prevent bleeding under the skin. A pressure dressing will then be applied.

Inclusion of women of childbearing potential: Women who are pregnant or lactating, and women of

childbearing potential will be excluded from the study. The PI will provide the PET center with documentation of non-childbearing potential status of female participants.

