Radiation Exposure: Participants in this sub-study will receive a target radiation exposure from three injections of ≤ 5 mCi of [¹⁸F]FPEB. This is equal to an effective dose of 0.930 rem. If a scan fails quality control, participants may be asked to repeat one [¹⁸F]FPEB PET scan. If a scan is repeated, participants will receive radiation exposure from four injections of ≤ 5 mCi of [¹⁸F]FPEB. This is equal to an effect dose of 1.24 rem.

Participants will also receive radiation exposure from either 3 low dose head CT scans or 3 transmission scans. If scans are completed on the High Resolution Research Tomograph (HRRT), participants will receive up to 0.0045 rem from transmission scans. If scans are completed on the mCT, participants will receive up to 135mrem (0.135 rem) from low dose head CT scans.

Participants who repeat a [¹⁸F]FPEB PET scan will receive radiation exposure from an additional low dose head CT scan or transmission scan for a total of 4 low dose head CT scans or 4 transmission scans. If scans are completed on the HRRT, these participants will receive up to 0.006 rem from transmission scans. If scans are completed on the mCT, these participants will receive up to 180mrem (0.180 rem) from low dose head CT scans.

The targeted amount of radiation exposure participants will receive from this study is an effective dose of 1.065 rem. The maximum possible radiation exposure participants will receive from participating in this study, if a scan is repeated, is an effective dose of 1.42 rem.

5. Genetic Testing N/A

A. Describe

- i. the types of future research to be conducted using the materials, specifying if immortalization of cell lines, whole exome or genome sequencing, genome wide association studies, or animal studies are planned

- ii. the plan for the collection of material or the conditions under which material will be received

- iii. the types of information about the donor/individual contributors that will be entered into a database

- iv. the methods to uphold confidentiality

B. What are the conditions or procedures for sharing of materials and/or distributing for future research projects?

C. Is widespread sharing of materials planned?

D. When and under what conditions will materials be stripped of all identifiers?

E. Can donor-subjects withdraw their materials at any time, and/or withdraw the identifiers that connect them to their materials?

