This study will involve 3 [¹⁸F]FPEB PET scan sessions. The targeted amount of radiation an individual participant may receive from this study is from a maximum of three injections of ≤ 5 mCi of [¹⁸F]FPEB plus three accompanying transmission scans or low dose head CTs.

Although each organ will receive a different dose, the amount of radiation exposure participants will generally receive during participation in this study is equal to an effective dose of 0.930 rem from [¹⁸F]FPEB and 0.0045 rem from transmission scans if scans are performed on the HRRT or 0.135 rem from low dose head CTs if scans are performed on the mCT. The total radiation exposure from all three scanning sessions would be 0.935 rem if scans are performed on the HRRT and 1.065 rem if scans are performed on the mCT.

In the case of quality control failure, participants may be asked to repeat one [¹⁸F]FPEB PET scan. In this case, the maximum amount of radiation exposure that a participant may receive from this study is 1.24 rem from four injections of ≤ 5 mci [¹⁸F]FPEB and .006 rem from transmission scans if scans are performed on the HRRT or .180 rem from low dose head CTs if scans are performed on the mCT. The total radiation exposure from all four scans is 1.246 rem if scans are performed on the HRRT and 1.42 rem if scans are performed on the mCT.

The amount of radiation participants will receive in this study is below the dose guidelines established by the FDA and monitored by the Yale-New Haven Hospital Radiation Safety Committee for research participants. This guideline sets an effective dose limit of 5 rem per year. (FDA 21 CFR 361.1; 5 rads per year for whole body, active blood forming organs, lens of the eye and gonads; 15 rads per year for other organs).

Risks Associated with IV Line Insertion

To minimize risks associated with blood draws and infusions, experienced medical personnel will do all the blood drawing procedures. At the PET Center the risks of bruising, clotting, and infection will be minimized by having venipuncture performed by trained and experienced personnel using aseptic technique. To avoid injury due to fainting, the catheter will be inserted when the participants are in a recumbent position. The blood draws during PET scanning sessions will be obtained from the already inserted catheter, to minimize discomfort.

11. **Minimizing Risks:** Describe the manner in which the above-mentioned risks will be minimized.

Risks Associated with Study Drug, BMS-984923

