4. **Background Information:** Provide a description of previous human use, known risks, and data addressing dosage(s), interval(s), route(s) of administration, and any other factors that might influence risks. If this is the first time this radiotracer is being administered to humans, include relevant data on animal models.

[¹⁸F]FPEB

The radiotracer [¹⁸F]FPEB has previously been used in human participants; 5 individuals at the Neurodegenerative Disorders (IND) in New Haven CT, and over 100 individuals at Yale University. No participants have reported any adverse event with this radiotracer. However, participants will be monitored carefully during and after the PET scan for any potential side effects.

The radiation dose estimates are based on the biodistribution data for [¹⁸F]FPEB in 6 healthy adults (3 men and 3 women) and calculated using OLINDA/EXM software ([Wong 2013](#)). Based on these numbers, the critical organ is the gallbladder wall (0.191 mGy/MBq, i.e., 0.708 rad/mCi). Another radiation dose study ([Kessler 2014](#)) also reported gallbladder wall (0.193 mGy/MBq, 0.714 rad/mCi) as the critical organ based on the biodistribution data in 9 healthy adults (5 men and 4 women). However, Kessler et al. reported the urinary bladder wall as the critical organ (0.258 mGy/MBq, 0.955 rad/mCi) when no voiding takes place prior to a 3.5 h period. Thus, the maximum allowable injection doses for [¹⁸F]FPEB to remain below the 21 CFR 361.1 dose limits for research participants are 5.2 mCi per single injection (calculations based upon the urinary bladder wall for a 3.5 h voiding), and 7 mCi per single injection (calculations based upon the gallbladder wall as the critical organs); 3 rads per single study for whole body, active blood forming organs, lens of the eyes and gonads; 5 rads for other organs per single study limit.

5. **Source:** Identify the source of the radiotracer to be used.

[¹⁸F]FPEB will be synthesized at the Yale University PET Center radiochemistry Laboratory under the supervision of Drs. [name] & [name].

6. **Storage, Preparation and Use:** Describe the method of storage, preparation, stability information, method of sterilization and method of testing sterility and pyrogenicity.

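### The protocol says radiation stays below the FDA limits it cites, but with the permitted repeat scan its own bladder-wall coefficient gives up to 19.1 rad against 15 rad per year

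*Combined protocol and SAP*

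**What the plan says.** Section I, item 4 (Receptor Occupancy Substudy) plans three FPEB PET scans per substudy participant and allows one more after a quality-control failure: "Each participant may be asked to repeat up to one" such scan. Each injection may be up to 5 mCi. Under PET Scan Procedures, "The scanning period is 0 - 120 min post injection". Nothing is said there about bladder voiding.

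The Radiation Exposure paragraph of that section puts the maximum, "if a scan is repeated, is an effective dose of 1.42 rem". Section I, item 10 repeats the three-scan and four-scan effective doses and then states that "The amount of radiation participants will receive in this study is below the dose guidelines established by the FDA". It names an annual effective-dose limit of 5 rem and, in the regulatory parenthesis, "15 rads per year for other organs".

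Organ doses appear only in Section II, A.4 (Background Information). Two dosimetry studies give gallbladder wall as the critical organ, at 0.708 and 0.714 rad/mCi. The second also "reported the urinary bladder wall as the critical organ (0.258 mGy/MBq, 0.955 rad/mCi) when no voiding takes place prior to a 3.5 h period". These coefficients are used only for single-injection ceilings: 7 mCi from the gallbladder wall and "5.2 mCi per single injection (calculations based upon the urinary bladder wall for a 3.5 h voiding" from the bladder wall.

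**The concern.** The compliance sentence follows directly after the four-scan maximum and carries no qualification, so it covers the repeat scan. It invokes organ limits as well as the effective-dose limit. Effective dose is a weighted whole-body quantity and says nothing about whether one organ stays under 15 rad. The protocol checks the bladder wall against the per-study limit but does not carry the same coefficient through to the annual limit.

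At stake is a safety assurance about healthy volunteers who gain no direct benefit. Only optional-substudy participants who receive a repeat injection are affected. No endpoint or dose-escalation rule depends on it.

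**Working it through.** **Inputs**

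- Bladder-wall coefficient, no voiding before 3.5 h: 0.258 mGy/MBq (Section II, A.4). Converted: 0.258 × 37 / 10 = 0.955 rad/mCi, as stated.
- Gallbladder-wall coefficients: 0.708 and 0.714 rad/mCi (Section II, A.4).
- Injections: three planned, four with a repeat, each up to 5 mCi (Section I, item 4).
- Limits: 5 rad per single study (Section II, A.4) and 15 rad per year (Section I, item 10), both for other organs.
- Participation lasts about 14 weeks (Section I, item 2), so the scans are summed within one year.

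**Reproducing the protocol's figures**

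- Ceiling = 5 rad / coefficient: 5 / 0.955 = 5.24 mCi (stated 5.2); 5 / 0.714 = 7.00 mCi (stated 7).
- Tracer effective dose: 0.930 rem / 15 mCi = 0.062 rem/mCi; × 20 mCi = 1.24 rem. Adding head CT: 0.930 + 0.135 = 1.065 rem and 1.24 + 0.180 = 1.42 rem. Adding transmission scans instead: 0.9345 rem (stated 0.935) and 1.246 rem.

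All of these agree with the protocol.

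**Cumulative organ dose = scans × mCi per scan × rad/mCi**

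| Organ | Scans | mCi each | Dose (rad) | % of 15 rad |
|---|---|---|---|---|
| Bladder wall (0.955) | 3 | 5 | 14.3 | 95.5 |
| Bladder wall | 4 | 5 | 19.1 | 127 |
| Bladder wall | 4 | 4.5 | 17.2 | 115 |
| Bladder wall | 4 | 4 | 15.3 | 102 |
| Bladder wall | 4 | 3.9 | 14.9 | 99 |
| Gallbladder wall (0.708 to 0.714) | 4 | 5 | 14.2 to 14.3 | 94 to 95 |

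**Break-even for four scans**

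- By activity: 15 / 0.955 = 15.7 mCi in total; / 4 = 3.93 mCi per scan.
- By coefficient at 5 mCi each: 15 / 20 = 0.75 rad/mCi, which is 1 − 0.75 / 0.955 = 21.5% below the no-voiding value.
- Room left after three full-activity scans without early voiding: 15 − 14.325 = 0.675 rad, or 0.675 / 0.955 = 0.7 mCi.

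Head CT and transmission doses are given only as effective dose and are left out of the organ figures.

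**The case against.** The 19.1 rad figure needs a repeat scan, the full 5 mCi every time, and no voiding before 3.5 h on all four occasions. Scanning ends at 120 min, leaving 90 min to void, and the two scheduled post-dose scans fall within supervised 24-hour urine collections. Repeats should be uncommon: post-dose scans are tied to their timepoints, and a synthesis failure before injection adds no dose. All of this makes the worst case less likely. None of it fixes when a participant voids or lowers the permitted activity.

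The strongest point is in Section II, A.4 itself. The study that supplies 0.955 otherwise names the gallbladder wall, at 0.714 rad/mCi, as critical. If critical means highest dose, the bladder coefficient in that study's base case is at most 0.714, and four full scans give at most 20 × 0.714 = 14.3 rad. This suggests that timely voiding would solve the problem. It remains an inference, because the base-case voiding schedule is not stated and the visible text does not require one.

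The safeguards also count. The radiation safety committee must approve before any scan (Section I, item 10), and items 4, 8 and 11 exclude people whose exposure would exceed FDA limits. Those exclusions are aimed at prior exposure and do not restrict a repeat within the study. Committee review does not correct the sentence.

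Finally, none of the protocol's stated figures that were checked is wrong, and its effective-dose comparison with 5 rem holds. The gap is an annual organ total that was never calculated. Operating procedures that are not visible may deal with voiding.

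**Conclusion.** The concern holds. For three scans, the protocol's own inputs put both organs under 15 rad, although the protocol does not present that total. For four scans, the gallbladder wall complies, but the bladder wall can reach 19.1 rad, 27% over. The plan as written therefore permits an exposure above a limit it says it meets.

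The size rests on 5 mCi at each injection and no voiding before 3.5 h, the condition the protocol chose for its own 5.2 mCi ceiling. The finding is that compliance has not been shown for the permitted maximum. It does not predict that any participant will exceed the limit. The reach is narrow, but this is a participant-safety statement and should be corrected.

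**What to change.** 1. In Section I, items 4 and 10, add cumulative bladder-wall and gallbladder-wall doses for three and four scans beside the effective-dose totals, stating the voiding assumption.
2. Qualify the compliance sentence for the four-scan case.
3. Make a repeat scan conditional on staying within 15 rad, by whichever route the radiation safety committee prefers:
   - (a) require voiding promptly after each 120 min scan and cite a bladder coefficient for that schedule of at most 0.75 rad/mCi at 5 mCi; or
   - (b) cap cumulative activity over four injections at about 15.7 mCi, an average of 3.9 mCi. This has to be planned from the first scan, because three full-activity injections leave only about 0.7 mCi.

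The cost is an amendment with matching consent wording and a short dosimetry table. Option (b) may mean lower injected activity per scan and so somewhat noisier images.

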The DSMB will meet following the last participant visit for each of the four dose cohorts. The PI will be responsible for scheduling the meetings (in-person or by teleconference) and to ensure that all materials needed for review are provided with sufficient time prior to the meeting. Each meeting will be divided into two parts. First, an open session in which the principal investigators may be present, at the request of the DSMB, to review the conduct of the trial and to answer questions from members of the DSMB. The focus in the open session may be on accrual, protocol compliance, and general toxicity issues. Following this session, a closed session involving only DSMB members will be held to allow the DSMB opportunity to discuss the general conduct of the trial and all outcome results, including toxicities and adverse events, develop recommendations, and take votes as necessary. A written report will be provided by the DSMB to the PI, IND holder ([name]), and sponsors (NIA, Alzheimer's Association). At minimum this will include a recommendation to continue the protocol as planned and an approval of the dose escalation for the next dose cohort. Protocol changes or discontinuation may also be recommended.

Safety Assessment and Dose Escalation Decisions

For the first 3 participants enrolled in the study, drug dosing will be conducted at a minimum of 48 hours between the first and second, and between the second and third participants. For subsequent cohorts, there will be at least 24 hours between dosing the first and second participants, and between the second and third participants, to allow for a 24-hour safety assessment review by the PI and medical monitor for each prior participant.

Determination of whether to open the next escalated dose cohort for enrollment will be made jointly by the PI, medical monitor, DSMB, and IND holder ([name]) after review of all available clinical,

safety, and PK data. Dose escalation (for each sequential cohort) will not occur until all participants in the prior cohort have completed the study. The DSMB will perform an independent review. In addition, the PI and medical monitor will make a determination independent from the IND holder. [name] will be consulted in scenarios where alterations to the planned dose escalation strategy are being considered. As the IND holder, [name] must also agree with a decision to proceed with dose escalation before the next cohort is dosed.

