Dose escalation decisions will be determined with the following approach. At the completion of each cohort, 0-72 h PK data will be used to assess the plasma exposure derived from the area under the curve (AUC) from 0-24 h. Our dose escalation decisions will be based on the human data relative to the rat 28 day GLP toxicology study to determine maximal NOAEL. In that study, the plasma exposure at NOAEL based on AUC (0-24h) was 192,000 ng*h/mL (see IB). Furthermore, the plasma exposure in corresponding Cynomolgus study was similar at 169,000 ng*h/mL.

The maximal doses for each cohort will be 10, 40, 70, 100, 150 and 200 mg. The human equivalent dose derived from the NOAEL dose in the 28D toxicology study in the most sensitive species (rat) is 140 mg. Thus, the starting dose is less than 10% of the 140 mg amount. Dose escalation in cohorts 2-6 will follow the plan above, but will be decreased based on the observed plasma exposure of the AUC (0-24 h) as detailed in the schedule below. The dose escalation for the next cohort will be based on the most recent cohort observed PK analysis as follows:

If plasma $AUC_{0-24h} < 24,000 \text{ ng}^*\text{h}/\text{ml}$ (12.5% NOAEL), then dose increase according to schedule
 If plasma $AUC_{0-24h} 24,000-48,000 \text{ ng}^*\text{h}/(12.5-25\% \text{ NOAEL})$, then dose increase maximum of 2 fold
 If plasma $AUC_{0-24h} 48,001-96,000 \text{ ng}^*\text{h}/\text{ml}$ (25-50% NOAEL), then dose increase maximum of 1.5 fold
 If plasma $AUC_{0-24h} 96,001-120,000 \text{ ng}^*\text{h}/\text{ml}$ (50-67.5% NOAEL), then dose increase maximum of 1.3 fold
 If plasma $AUC_{0-24h} > 120,000 \text{ ng}^*\text{h}/\text{ml}$ (>67.5% NOAEL), then stop escalation

Any serious adverse events or other safety concern might also constitute a rationale to stop or reduce escalation.

Criteria for intervention discontinuation

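### The stop-escalation threshold of 120,000 ng*h/mL is 62.5% of the stated rat NOAEL exposure, but the protocol labels it 67.5%, which is 129,600 ng*h/mL

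*Combined protocol and SAP*

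**What the plan says.** The rule is in the protocol, Section I, item 12, under Safety Assessment and Dose Escalation Decisions.

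- **Basis.** The section states "Our dose escalation decisions will be based on the human data relative to the rat 28 day GLP toxicology study to determine maximal NOAEL".
- **Reference exposure.** The rat figure used throughout the schedule is given as follows: "the plasma exposure at NOAEL based on AUC (0-24h) was 192,000 ng*h/mL". A Cynomolgus figure of 169,000 ng*h/mL is given for comparison.
- **How the rule is applied.** "The dose escalation for the next cohort will be based on the most recent cohort observed PK analysis as follows".
- **Planned doses.** "The maximal doses for each cohort will be 10, 40, 70, 100, 150 and 200 mg". These are ceilings, to be lowered according to observed exposure.
- **Tiers.** Below 24,000 ng*h/mL (12.5%), follow the schedule. From 24,000 to 48,000 (12.5-25%), at most double the dose. From 48,001 to 96,000 (25-50%), at most 1.5-fold. From 96,001 to 120,000, the label is "50-67.5% NOAEL), then dose increase maximum of 1.3 fold". Above 120,000, it is "67.5% NOAEL), then stop escalation".
- **Who decides.** The decision to open the next cohort "will be made jointly by the PI, medical monitor, DSMB, and IND holder".

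**The concern.** Every cut-point is written twice, once in ng*h/mL and once as a percentage of the NOAEL exposure. If both are right, each pair must give the same number. The top pair does not, and it is the pair that stops escalation. Nothing in the section ranks one expression above the other, and the lead-in frames the whole scheme relative to the rat study, so the percentage cannot simply be ignored.

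This is the first administration of the drug to humans, and the AUC schedule is the only numerical escalation or stopping rule; the other grounds for stopping are matters of judgement. The protocol puts the human equivalent of the rat NOAEL dose at 140 mg, yet cohorts 5 and 6 are planned at 150 and 200 mg. At those doses observed exposure is the main quantitative safeguard. The parties who must agree on escalation need a single number.

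**Working it through.** **Inputs**, all from Section I, item 12: rat NOAEL AUC(0-24h) 192,000 ng*h/mL; Cynomolgus 169,000 ng*h/mL; the four cut-points and their labels; planned doses 10, 40, 70, 100, 150 and 200 mg.

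**1. Reproduce the labels.** Percentage = cut-point / 192,000.

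| Cut-point (ng*h/mL) | Calculated | Printed |
|---|---|---|
| 24,000 | 12.5% | 12.5% |
| 48,000 | 25.0% | 25% |
| 96,000 | 50.0% | 50% |
| 120,000 | 62.5% | 67.5% |

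Three agree exactly, which confirms 192,000 as the denominator and rules out rounding. The fourth is wrong in both lines where it appears.

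**2. Try other denominators for the top pair.**

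- Cynomolgus: 120,000/169,000 = 71.0%. The other three would become 14.2%, 28.4% and 56.8%, so this breaks the labels that do agree.
- Mean of the two species: 120,000/180,500 = 66.5%.
- Denominator needed for 67.5%: 120,000/0.675 = about 177,778, which the protocol does not state.

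None of these reproduces the printed label.

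**3. Size of the gap.** 0.675 x 192,000 = 129,600. The difference is 129,600 - 120,000 = 9,600 ng*h/mL, which is 5 percentage points of the NOAEL exposure and 9,600/120,000 = 8% of the printed cut-point.

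**4. What turns on it.** The two expressions disagree only for a cohort AUC above 120,000 and up to 129,600. There the AUC figure stops escalation and the percentage puts the cohort in the 1.3-fold tier.

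| Current dose | Planned next dose (ratio) | 1.3-fold cap |
|---|---|---|
| 70 mg | 100 mg (1.43) | 91 mg |
| 100 mg | 150 mg (1.50) | 130 mg |
| 150 mg | 200 mg (1.33) | 195 mg |

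Each planned ratio exceeds 1.3, so the cap would set the dose.

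**5. Exposure after such a step.** Assuming AUC proportional to dose, a 1.3-fold step gives 1.3 x 120,000 = 156,000 to 1.3 x 129,600 = 168,480 ng*h/mL. That is 81% to 88% of the rat figure and 92% to 99.7% of the Cynomolgus figure.

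**The case against.** The strongest reply is that only one stopping exposure is printed. The figure 120,000 appears in both lines, leads each condition, gives contiguous bands and is the stricter value; 129,600 is nowhere in the protocol and is only implied by a label in parentheses. A careful reader would apply 120,000. This stands as a reason to think 67.5% is a slip for 62.5%. It does not supply the missing statement of which figure governs.

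A second reply is that some of the dose examples may be unreachable. If AUC is proportional to dose, an AUC in the disputed band at 100 mg implies about 48,000 to 51,840 at 40 mg. The 1.5-fold cap would then send cohort 3 to 60 mg, cohort 4 to 90 mg and any next cohort to 117 mg, so no 100 mg cohort would occur. Likewise a band value at 70 mg implies about 68,600 to 74,100 at 40 mg, so cohort 3 would be at 60 mg, not 70. Among the three planned doses in the table above, only the 150 mg case survives. This arithmetic is right, but human pharmacokinetics are unknown in a first-in-human study. Even under proportionality, the protocol's own caps can lead into the band at reduced doses. With 1,400 ng*h/mL per mg, the cohorts run 10 mg (14,000), 40 mg (56,000), 60 mg (84,000) and 90 mg (126,000), and the last falls in the band. Also, 91 mg cannot be made from the 5, 50 and 100 mg capsules; 90 mg is the practical limit.

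A third reply is that harm is limited. The fold values are maxima, several parties must agree, any safety concern can stop escalation, and under proportionality a 1.3-fold step stays below both animal exposures, though at the top of the band only just below the Cynomolgus one. All of this stands. It limits the consequence but does not settle which threshold applies.

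**Conclusion.** The concern holds. The top cut-point is mislabelled in both lines: 120,000 ng*h/mL is 62.5% of the stated rat NOAEL exposure, and the printed 67.5% corresponds to 129,600. That finding needs no assumption beyond the protocol's own reference value, which the three other cut-points confirm.

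The practical effect is confined to a band of 9,600 ng*h/mL, in which the choice is between stopping and escalating by up to 1.3-fold. Which doses could be involved depends on human pharmacokinetics not yet known. Sample size, alpha and the descriptive analyses are unaffected. It should nevertheless be corrected, because it is a wrong figure in the stopping rule of a first-in-human study and should not be left to inference at an escalation meeting.

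**What to change.** In Section I, item 12, change 67.5% to 62.5% in both the 1.3-fold line and the stop line. Add one sentence stating that the ng*h/mL value governs and the percentage is for information, so that escalation stops above 120,000 ng*h/mL.

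If the sponsor, medical monitor and DSMB confirm that 67.5% was intended, change 120,000 to 129,600 in both lines instead. The first option is the stricter and should be the default.

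The cost is one number in two lines plus a sentence, made by amendment. No further data or participants are needed.
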